3.5 Sensitivity Analyses

The primary analysis will be repeated for each of the following modifications:

1. **Adjusted Analyses:** We will use Generalized Estimating Equations to compare percentage of negative UDTs with adjustment for the following covariates: (see table below)
2. **Missing Data Analyses:** The primary analysis will be repeated using multiple imputations for missing urine samples (rather than assuming all missing are opioid positive). All covariates listed below will be used in the imputation model provided they have less than 20% missing. (See additional details on missing data in [Section 3.8.](#))

3. **Per-protocol Analyses:** The primary analysis will be repeated excluding patients who drop out of the study or are not compliant with study protocol (e.g., submitted 7 or less videos during the first 4 weeks of study involvement). In addition, analyses will use the number of uploaded videos as a measure of compliance to determine whether there is a dose-response effect.

4.

Covariate Table	
1. Site	Seattle or Boston
2. Age	Years
3. Sex	Male, Female
4. Race	Caucasian vs. Non-Caucasian
5. Hispanic Ethnicity	Yes or No
6. Education	Less than High School, High School, Some College, Bachelor's degree or higher
7. Prior Buprenorphine Treatment	Yes or No
8. Homelessness	Yes or No

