Development and Evaluation of Video-Based Directly Observed Therapy for Office-Based Treatment of Opioid Use Disorders with Buprenorphine

NCT03779997

APRIL 4, 2021

TAAB SAP Table of Contents

- 1 Study Overview and Design 2
 - 1.1 Target Population..... 2
 - 1.1.1 Study Sites..... 2
 - 1.1.2 Inclusion/Exclusion Criteria 2
 - 1.2 Group Allocation – Randomized..... 3
 - 1.3 Study Outcomes..... 3
- 2 Sample Size Determination 3
- 3 Analysis Plan..... 4
 - 3.1 Analysis Parameters 4
 - 3.2 Primary Analysis (Percentage Opioid Negative Urine Tests) 4
 - 3.3 Secondary Analysis (Retention - Week 12)..... 5
 - 3.4 Exploratory Hypotheses..... 5
 - 3.5 Sensitivity Analyses..... 7
 - 3.6 Additional Model Selection Analyses..... 8
 - 3.7 Sub-group Analyses 8
 - 3.8 Missing Data..... 8
- 4 Data Monitoring 9
 - 4.1 Interim and Safety Analyses 9

Trial of Adherence Application for Buprenorphine Treatment (TAAB) Study Protocol and Statistical Analysis Plan

1 Study Overview and Design

The objective of this study is to compare an innovative mobile health (mHealth) platform to support patients treated for opioid use disorder (OUD) with buprenorphine to treatment-as-usual (TAU). The application will provide video-based directly observed therapy (video-DOT) which may result in better health outcomes for patients and less public health risk for diversion.

All participants will follow the same visit schedule. Interviews will occur at baseline (Week 0) and the final visit (Week 12) and assessments will include questions on current and prior substance use, treatment history, medication adherence, drug diversion, general physical and mental health and treatment satisfaction. A point of care urine drug test (UDT) will also be administered at baseline and all weekly visits which will assess for opioids and other substances. Research staff will review the electronic medical record at baseline and week 12 to assess engagement in treatment. Additionally, at 24 weeks post-enrollment the research staff will complete a review of the electronic medical record and record engagement in clinic treatment, changes in buprenorphine treatment during the study period and the results of clinical urine drug testing if available.

Study type: Pilot Randomized Controlled Trial of a Behavioral Intervention – Video-DOT smartphone application where participants will be asked to record one daily video of themselves confirming daily ingestion of their prescribed buprenorphine.

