3.2 Primary Analysis (Percentage Opioid Negative Urine Tests)

The primary analysis is performed to test the following hypothesis:

Primary Hypothesis: Patients in video-DOT arm will have higher percentage of weekly UDTs negative for opioids compared to TAU during the 12 -week intervention period.

Analyses will be done according to the intent-to-treat principle which includes all randomized patients regardless of their compliance with the study protocol. To evaluate the primary hypothesis, we will compare percentage of negative UDTs between the two groups using Generalized Estimating Equations (GEE). Missing urine samples will be assumed to be positive*.

* **NOTE:** As of 3/13/2020 phone visits have occurred at both sites due to the COVID-19 outbreak. For follow-up and final assessment visits by phone, a study UDT sample was not collected. If a clinical UDT result is also not available for a particular phone visit, then the participant’s UDT data for that visit is excluded from the primary analysis.

Primary Outcome Variables

12 Research-UDTs for 5 Opioid Assays (F/U Visits 1-11, and Final):

- Negative for opioids* = negative for the following: Morphine (i.e., “udt_he”), Methadone, Oxycodone, Fentanyl
* Propoxyphene assay was in the original UDTs (Alere iCup); New UDT (Identify Diagnostics) does not include it. Will not include this data in the analysis. Dates new UDT’s first started being used: BMC – 11/6/2019, UW – 11/8/2019.

- (1) On 2/11/2020 a decision was made to code a study UDT as negative if at least one substance was missing but the rest were negative.
 - (a) **Note:** First check the clinical UDT to supplant a missing value. I.e., If the clinical UDT is also missing for that same substance, code the test as negative. If the clinical UDT

is positive for the particular substance that is missing from the study UDT, then code that test as positive.

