3.8 Missing Data

All efforts will be made to complete study visits/procedures and avoid missing data. However, we anticipate there will be missing data, in particular for the primary outcome. As has been the convention in other studies, we will assume that missing UDT results are positive (unless a visit was conducted by phone due to COVID-19). However, we will also conduct analyses to better understand the nature of missing data and carry out multiple imputation analysis in order to determine the impact of missing UDTs.

We will assess missing data by comparing baseline characteristics between participants lost to follow-up (who are missing data on the primary or secondary outcome) versus those who are not.

Missing data patterns will also be evaluated including the frequency and percentage of those missing for each variable and the distribution of the number of variables missing. Patterns of missing urine samples will be described and compared between treatment arms.

Data collected to the point of lost to follow-up will be compared to the data of those who complete the study to examine possible missing data mechanisms, e.g., missing completely at random (MCAR), missing at random (MAR), or not missing at random (NMAR).

Sensitivity analyses using multiple imputation will be performed to assess the possible impact of missing data on the study results for the primary and secondary analyses. Imputation models will include the baseline covariates listed in the table above as well as intermediate outcomes as appropriate (e.g., for 24-week outcomes, the 12-week outcomes can be used in imputation models).

4 Data Monitoring

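### The only per-protocol compliance criterion that the plan names can remove patients from the video-DOT arm alone, and the video dose-response analysis names no patient set

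*Combined protocol and SAP*

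**What the plan says.** The primary analysis in section 3.2 is intent-to-treat and "includes all randomized patients regardless of their compliance with the study protocol". There, "Missing urine samples will be assumed to be positive". Section 3.8 repeats this: "we will assume that missing UDT results are positive (unless a visit was conducted by phone due to COVID-19".

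Section 3.5 opens with "The primary analysis will be repeated for each of the following modifications". Item 3, the per-protocol analysis, works by "excluding patients who drop out of the study or are not compliant with study protocol (e.g., submitted 7 or less videos" in the first 4 weeks). It then says that analyses will "use the number of uploaded videos as a measure of compliance to determine whether there is a dose-response effect". That sentence gives no patient set, model, time window or missing-data rule. Multiple imputation is a separate modification (item 2) and is not combined with item 3.

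Sections 1 and 1.2 place the video application in the video-DOT arm only, with one video a day. Section 1 also says "All participants will follow the same visit schedule", so a criterion common to both arms could be written, but none is.

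**The concern.** The dropout exclusion applies to both arms. The video criterion cannot: applied literally to TAU it would remove everyone, because TAU patients upload nothing. In practice it therefore removes low uploaders from video-DOT and leaves their TAU counterparts in. If patients who upload little early on are also less stable, the video-DOT arm is enriched for stable patients and the comparison is no longer randomised.

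The dose-response sentence has a different problem. A patient who leaves stops uploading and, under the missing = positive rule, has all later tests scored as opioid-positive. One event lowers both variables. Section 3.8 expects this to matter: "we anticipate there will be missing data, in particular for the primary outcome".

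Item 3 is the only place where the plan relates video use to the primary outcome. With a stated power of 69%, a non-significant primary result beside a favourable per-protocol or dose-response result is a realistic outcome, and that pattern can arise with no effect.

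**Working it through.** **Inputs from the documents.** 80 patients, about 40 per arm (section 1.2); 70% complete, so 0.70 × 40 = 28 completers per arm; 50% negative in TAU; 69% power for 20 points (section 2); level 0.05 (section 3.1).

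**Assumed, because the documents are silent.** How often patients upload, how uploading relates to stability, and the patient-level SD.

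**The plan's power figure.** It cannot be reproduced directly, because no SD or within-patient correlation is stated. It can be used to back out an SD. With power = Φ(0.20 / (SD × √(2/n)) − 1.96) and n = 28, SD = 0.305 gives 0.305 × 0.267 = 0.0815; 0.20 / 0.0815 = 2.45; Φ(0.49) = 0.69. With n = 40 the SD would be 0.364. The figure is plausible, and nothing below depends on its being right.

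**Per-protocol bias in closed form.** Let q be the share of video-DOT completers who fail the video criterion, and g the amount by which their percentage negative falls below that of those who pass. With no effect, TAU completers average (1 − q)P + q(P − g) = P − qg, where P is the mean of those who pass. The retained video-DOT patients average P. The bias is q × g. The standard error is 0.305 × √(1/28 + 1/(28(1 − q))).

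| q | g (points) | Bias (points) | Chance of significance favouring video-DOT (nominal 2.5%) |
|---|---|---|---|
| 10% | 10 | +1 | 3.3% |
| 20% | 20 | +4 | 6.7% |
| 30% | 30 | +9 | 16.9% |
| 40% | 30 | +12 | 24.7% |

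For the second row: 0.305 × √(1/28 + 1/22.4) = 0.0864; 0.04 / 0.0864 = 0.46; 1 − Φ(1.96 − 0.46) = 0.067. If g = 0 the bias is zero whatever q is.

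**Per-protocol bias by null simulation.** 40 per arm, 30% dropout, 50% negative, Welch test on patient percentages as a stand-in for the planned GEE. A latent stability drives urine results and dropout, and upload propensity is correlated with it.

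- 29% of video-DOT at 7 or fewer videos: +2.0, +4.2 and +6.1 points, with 6%, 8% and 12% two-sided false positives, at correlations 0.2, 0.4 and 0.6. At zero correlation there is no bias and 5%. Separately coded repeats gave +2.0 to +2.5, +3.9 to +5.1 and +5.8 to +7.9 points.
- 9% low uploaders: +0.1 to +1.0 points and 4-5% false positives (a repeat gave +0.6 to +1.4 and 5-6%).
- 15%: +0.9 to +2.9 points and 5-6%.
- 40%: +2.8 to +8.3 points and 5-18%.

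The simulation agrees with the formula. In the 29% case, 21-22 of 28 video-DOT completers remain, so q is about 1 − 21.5/28 = 23%, and a bias of +4.2 corresponds to g of about 4.2 / 0.23 = 18 points.

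**Dose-response with no effect and uploads unrelated to opioid use** (Pearson test, nominal 5%):

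| Patient set and missing-data rule | False positives |
|---|---|
| Video-DOT, dropouts kept, missing = positive | 46% (26-95% over assumed upload patterns) |
| TAU pooled in at zero videos, missing = positive | 24% (14-33%) |
| Video-DOT, dropouts kept, observed tests only | 12% (4-35%) |
| Video-DOT completers, no missed visits | 4-6% |
| The item's per-protocol set, no missed visits | about 5-6% |

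If completers miss 11%, 13% or 19% of visits, more often when they upload less, missing = positive gives about 8%, 20% or 32%, and observed tests about 5%.

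**What restriction does not remove.** At upload-stability correlations of 0.2, 0.4 and 0.6, completers still give 13%, 40% and 80% false positives. The smaller per-protocol set, with its narrower upload range, gives about 9%, 20% and 45%. If dropout depends on both stability and uploading (correlation 0.5 with each), selecting completers creates a false negative association: about 9-10% significant in the wrong direction.

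**The case against.** Item 3 is labelled per-protocol and sits among sensitivity analyses in a pilot whose primary analysis is intent-to-treat. The example is introduced as one of possibly several criteria. No upload rate or correlation is given, and with 15% or fewer low uploaders the error rate hardly moves. All of this stands, and it limits the importance of the point. It does not supply a criterion for TAU.

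A reader might infer that the plan as written gives a 46% false-positive rate for dose-response. The documents do not support that. The sentence follows directly on the exclusion of dropouts, so using the per-protocol set is a natural reading, and there the mechanical association largely disappears. Pooling TAU at zero videos is a further reading that the text does not state. Carry-over of missing = positive is inferred from the section 3.5 lead-in and from section 3.8; the sentence itself does not say so. What stands is that the patient set and the missing-data rule are not named and that the choice matters.

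A reader might also infer that the per-protocol comparison must be biased, or that item 3 drives the Phase III decision. The first needs low uploaders to have worse urine results. On the second, section 2 bases the Phase III sample size on the pilot's results in general and does not single out item 3.

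The complier estimate can be called a refinement, since it tests essentially the same null as intent-to-treat. That is fair. Its value is as an effect estimate for patients who use the application that keeps the randomised comparison.

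**Conclusion.** The point holds with modest importance. The named compliance criterion can act only on video-DOT. With no effect it shifts the per-protocol comparison by about +2 to +8 points if roughly 29% are low uploaders and the upload-stability correlation is 0.2 to 0.6, and by close to zero if low uploaders are few or uploading is unrelated to stability. These are assumed conditions, and the sizes come from stand-in tests, not the planned GEE.

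For dose-response the fault is an unnamed patient set and missing-data rule. The false-positive rate when uploads are unrelated to use runs from about 5-6% to about 46% depending on how the sentence is read. On any reading, confounding by engagement keeps the result from being causal. The primary analysis is unaffected.

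**What to change.** **1. Per-protocol comparison.** List each compliance criterion and the arm or arms to which it applies. Keep the comparison, but label it non-randomised. Report beside it a complier average causal effect in all randomised patients: randomisation as instrument, complier = more than 7 videos in the first 4 weeks, TAU = 0, primary urine-test rules. The estimate is the intent-to-treat difference divided by the share of compliers in video-DOT. State the exclusion assumption, that being assigned the application has no effect in patients with 7 or fewer videos, and add a run with complier = any video.

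Cost: SAP wording and one short model. The interval is wider (SD about 11 points against about 8 for intent-to-treat; 7.8 / 0.71 = 11.0), and there is no new test of the null. In the null simulations the estimate stayed within about 0.6 point of zero with 29% low uploaders. If the exclusion assumption fails, the estimate is too high. Suppose low uploaders get half of a 20-point effect: intent-to-treat is 0.71 × 20 + 0.29 × 10 = 17.1, and 17.1 / 0.71 = 24 instead of 20. The any-video run would read about 17, the average over all uploaders.

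**2. Dose-response.** Run it within video-DOT only, with TAU not pooled at zero videos, in patients who did not drop out, and on observed urine tests without missing = positive. Report it as descriptive and non-causal, because confounding by engagement remains and selection on completion can bias it in either direction. Cost: about 28 of 40 patients remain. This point takes no position on covariate adjustment here; section 3.5 attaches its covariate table to items 1 and 2 only.

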3.6 Additional Model Selection Analyses

Additional analyses will be completed using different models (linear and logistic) to determine which models will be best suited for a future definitive trial.

3.7 Sub-group Analyses

The primary analysis will be repeated with interaction terms between treatment arm and each of the following sub-group variables:

- a. Site (Boston and Seattle)
- b. Gender (Men vs. Women)
- c. Age (based on median split)
- d. Baseline homelessness

Results will be reported as treatment effect estimates for each sub-group with 95% confidence intervals and tests of the null hypothesis with overall level of significance 0.05 and Bonferroni adjustment for multiple comparisons. In addition, a significance test of the interaction between treatment and each sub-group variable will be conducted at significance level 0.05.

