3.1 Analysis Parameters

Results of the Generalized Estimating Equations (GEE), Poisson regression, and unequal variance t-test analyses will be reported with 95% confidence intervals and test of the null hypothesis at a significance level of 0.05.

GEE was selected because it accounts for correlation between observations on the same patient over time without requiring assumptions about correlation structure by using “robust” variance estimates.

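### Age is cut at its sample median for the age-by-arm interaction, and the GEE robust variance has no small-sample correction for subgroups of about 20 per arm

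*Combined protocol and SAP*

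**What the plan says.** Section 3.7 states that "The primary analysis will be repeated with interaction terms between treatment arm and each of the following sub-group variables", and lists site, gender, age and baseline homelessness. It then sets two separate rules.

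- Treatment effects within each subgroup are reported with 95% intervals and "tests of the null hypothesis with overall level of significance 0.05 and Bonferroni adjustment for multiple comparisons". The Bonferroni divisor is not given.
- In a further sentence, "a significance test of the interaction between treatment and each sub-group variable will be conducted at significance level 0.05".

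The age item reads "Age (based on median split"). The covariate table in section 3.5 lists age in years.

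Section 3.1 chooses GEE because it "accounts for correlation between observations on the same patient over time without requiring assumptions about correlation structure", and does so "by using “robust” variance estimates". No small-sample correction, reference distribution or link function is named. Section 1.2 gives a target of 80 participants, about 40 per site, with treatment assignments split half and half within site.

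**The concern.** Two choices are weaker than they need to be.

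First, dichotomising a continuous modifier discards information. Interaction power is already scarce in a trial with a stated 69% power for its main effect (section 2). The cut-point also depends on who happens to enrol, so a later trial could not reproduce it exactly.

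Second, the robust variance is a large-sample device. With few participants it is biased downwards, and a normal reference makes this worse. The within-subgroup tests are where the counts are smallest, and they are the tests for which the plan states an overall level.

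At stake is how far the subgroup results can be trusted when the Phase III trial is planned: a real age trend is harder to see, and a within-subgroup effect may be declared somewhat more often than stated.

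**Working it through.** **Inputs.** From the documents: N = 80, about 40 per site, half per arm, so about 20 per arm per site (1.2). A median split of age also gives about 20 per arm. There are four subgroup variables with two levels each (3.7), 12 urine tests per participant (1.3) and 50% opioid-negative in TAU (2). Assumed: two-sided tests, a Bonferroni divisor of 8, independence working correlation, an equal number of tests per participant, and 30% or 50% prevalence for one level of gender and of homelessness. Equal numbers are only approximate, because some COVID-19 phone visits are excluded (3.2).

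**1. The plan's own figure.** Eight within-subgroup tests at 0.05/8 = 0.00625 each give 8 × 0.00625 = 0.05. The stated overall level is reproduced nominally.

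**2. Real level of one test, identity link.** In this layout the GEE estimate is a difference in participant means. The uncorrected sandwich divides by n rather than n − 1, so the standard error is too small by √((n−1)/n). Against a normal reference, the real level is P(|t with 2n−2 df| > z·√((n−1)/n)).

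- n = 40 per arm (whole trial): 1.96 × 0.9874 = 1.935 on 78 df, giving 5.7%.
- n = 20 per arm: 1.96 × 0.9747 = 1.910 on 38 df, giving 6.4%.

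**3. The eight Bonferroni tests, identity link.** At 0.00625, z = 2.734. With n = 20, 2.734 × 0.9747 = 2.665 on 38 df gives 1.123% per test. If the tests are independent, 1 − (1 − 0.01123)^8 = 8.6%. If gender and homelessness each split 12/28 per arm, the per-test levels there are 1.57% and 0.96%, and 1 − 0.98877^4 × 0.98429² × 0.99039² = 9.2%.

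**4. Dependence on the link.** Null trials were simulated with 80 participants and 12 beta-binomial tests each (within-patient correlation 0.54, 6,000 trials per setting). Chance of at least one false positive among the eight tests:

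| Link | Uncorrected, normal reference | n − 1 divisor, t reference |
|---|---|---|
| Identity | 8.1–9.0% | 5.1–5.4% |
| Logit | 5.5–6.5% | 2.9–3.3% |
| Log | 3.6–4.2% | 1.6–1.9% |

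With correlations from 0.3 to 0.7 on the identity link, single subgroup tests at nominal 5% ran at about 6–7%, and up to about 8% in the smallest groups at 30% prevalence.

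**5. Age.** If age is normal and the modification linear, the split has relative efficiency 2/π = 0.64. To illustrate, assume a slope of 12 percentage points per SD of age. Take the participant-level SD that matches the stated 69% power at 40 per arm: 0.20 / ((1.96 + 0.496) × √(2/40)) = 0.364.

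- Continuous age: standard error 2 × 0.364/√80 = 0.0814; 0.12/0.0814 = 1.47; power Φ(1.47 − 1.96) = 31%.
- Median split: 1.47 × √0.64 = 1.18; power Φ(1.18 − 1.96) = 22%.

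Simulation gave about 29–30% against 20–21%.

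**6. The interaction tests.** Four independent tests at 0.05 give 1 − 0.95^4 = 18.5%.

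**The case against.** A reader might infer that the four interaction tests break the promised overall level. They do not. The words "overall level of significance 0.05 and Bonferroni adjustment for multiple comparisons" govern the within-subgroup tests. The interaction tests come in a separate sentence with their own per-test 0.05, and no family-wise level is stated for them. The 18.5% is correct if the tests are independent, but it contradicts nothing in the plan. Requiring 0.0125 per test would cut power for a 20-point interaction from about 23% to about 10% (at SD 0.364). That is a trade-off, not a repair.

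A reader might also suppose that every subgroup has 20 per arm or fewer, and so expect much larger inflation. With 12 per arm in all eight groups, the formula in step 3 gives 11.9%. This cannot occur: the two levels of each variable must together make up about 40 per arm, so a level with 12 has a complement of about 28.

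The strongest remaining objection concerns the link. Section 3.6 lists linear and logistic models as additional analyses, which suggests, without settling it, that the primary model is neither. On a log link the eight tests are not inflated at all. This stands, and it makes the variance point conditional.

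On age, the split is pre-specified, and age in years serves adjustment and imputation in section 3.5, so the plan does not contradict itself. The 64% and the power figures rest on assumptions, and power is low either way. All of this stands too. What remains is that a more informative form of a variable already collected is available at almost no cost.

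**Conclusion.** Two modest improvements are warranted; neither corrects an error of fact.

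- **Age.** The median split keeps about 64% of the information, assuming normal age and linear modification.
- **Variance.** If the link is identity, the uncorrected robust variance puts a nominal 5% subgroup test at about 6–7%, and the eight-test family at about 8–9% instead of 5%. On logit the family runs at about 5.5–6.5%, and on log it is not inflated. These figures assume a divisor of 8. The gender and homelessness splits are not in the documents.

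The importance is low: these are subgroup analyses of a pilot, and no decision rule in the plan turns on them. The unadjusted interaction tests are consistent with what section 3.7 states.

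**What to change.** - In section 3.7, test the age-by-arm interaction on age in years and keep the median split for displaying effects. Say whether the two age-half effects are still formally tested, since that sets the Bonferroni count (eight, or 8 − 2 = 6).
- In section 3.1, specify a small-sample-corrected robust variance (for example Mancl-DeRouen) with a t reference for the GEE and subgroup models. State the link alongside it, because the size of the problem depends on it.
- Optionally, label the four interaction tests exploratory and note the 18.5%. No stricter threshold is needed.

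The cost is SAP wording and a software option. The age test takes on a linearity assumption. Intervals widen slightly. With 20 per arm on the identity scale, an n − 1 divisor with t gives (2.024/1.96) × √(20/19) = 1.06 times the width, and Mancl-DeRouen gives (2.024/1.96) × (20/19) = 1.09. Mancl-DeRouen is then a little conservative: P(|t with 38 df| > 2.024 × √(20/19)) = 4.5%. On logit or log links the correction makes the subgroup tests conservative, as the table under the working shows.
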